The Hunter has been very fortunate that collaboration with the Australian Institute of Neuro-rehabilitation (AIN) has procured the purchase of a REX exoskeleton (HELLEN: Hunter’s Exoskeleton for Lower Limb Exercises and Neuro-rehabilitation) and motor vehicle for transport, through a donation from the Newcastle Permanent Charitable Foundation. This is the first purchase of this robotic device in Australia.

There is, to date, no published clinical research evaluating the use of the REX Bionics exoskeleton in patients with MS. The vast majority of anecdotal evidence is also in relation to the use of the REX with spinal cord injured patients. Therefore, there is a need for independent research to establish the feasibility, acceptability and efficacy of lower limb robotics as a potential rehabilitation modality in the MS population.

We anticipate that this pilot study will provide the preliminary data required about safety, feasibility and effect size estimates, which is necessary for progression to a larger randomised trial, if warranted. The results of this trial will complement those from the clinical trial currently underway by this research team investigating the merit of this robotic exoskeleton in the Acquired Brain Injured population.

Objectives

The aim of this project is to examine the potential benefits and applicability of using HELLEN as an adjunct tool for neurorehabilitation in MS, as well as highlighting any barriers and risks to its potential use in this population. It is anticipated that this pilot data will assist in establishing priorities and directing further research in this field.

Trial Design

A phase 1 pre-post intervention trial with 12 week baseline control. This study design has the advantage of allowing all recruits in the study to receive the robotic exercise intervention. We aim to recruit 20 participants in this first stage pilot trial.

Study Setting

The trial will operate at one site only, at the University of Newcastle. A research room has been purpose built for this research in the Hunter Building with designated parking space for participants.

Eligibility Criteria

Inclusion Criteria:

1. Diagnosis of MS
2. Resident of the Hunter region over the age of 18 years
3. Severe mobility impairment whereby the participant is reliant on a mobility aid or other people for upright activities (Scores >6 on the Expanded Disability Status Scale)

Exclusion Criteria

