1. Weight >100kg or <40kg; height >6'4" or <4'8" (criteria set by the REX Bionics)
2. Pregnancy
3. Unstable or severe cardiac or respiratory conditions
4. Recent fractures in lower limbs/pelvis/spine
5. Significant cognitive impairment (<19 on MoCA)
6. Any medical condition which limits the ability to exercise in an upright position

The treatment will only be delivered by REX trained Physiotherapists. Researchers, [name] and [name] have both completed the full 3 day training course and attained competency accreditation.

Intervention

The intervention will involve 2 sessions of exercise therapy per week for 12 weeks. Each session will be up to 1 hour duration and will consist of half an hour of individualised therapy, prescribed and administered by a physiotherapist, including upright weight-bearing exercise facilitated by HELLEN as tolerated by the patient. This may be a combination of sit to stand practise, standing tolerance, weight shift, trunk control exercises, stepping practise, side stepping, squats, upper limb exercises and gait practise. These exercises will be individually tailored to meet the abilities and needs of the client. Participants will also be provided with a home exercise program

relevant to their treatment, which will be assessed and updated throughout the trial as required.

Interventions will only be progressed according to the individual participants' abilities as deemed appropriate by the administering physiotherapist. Interventions will be modified or ceased if, in communication with the participant, the researchers deem that this is necessary.

Outcomes

The timepoints for assessment of outcome measures are:

Week 0: Assessment and assignment to waiting list

Week 12: Commencement of therapy phase

Week 18: Mid- therapy assessment phase

Week 24: End of therapy phase

Week 36: Follow-up phase, 12 weeks after completion of intervention

Participants will be screened for eligibility and baseline measurements will be taken before participants are assigned to a 12 week waitlist. The primary outcome of interest is functional ability as measured by the Motor Assessment Scale. Secondary outcomes include a range of impairment, mood, fitness, and quality of life measures as listed below:

All assessment forms are attached and include:

1. Medical screening form: to determine eligibility for exercise and suitability of the robotic device

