2. Demographic information: Standard demographic and MS information including Kurtzke Expanded Disability Status Scale (EDSS)
3. Cognitive screen MoCA
4. Mood HADS
5. Attitude towards robotic therapy questionnaire
6. Routine physiotherapy assessments using standardised outcome tools: fatigue (FAS), function (MAS and sit to stand test), spasticity (Tardieu), quality of life (SF8), balance (functional reach), independence (Barthel Index), fitness (O2 consumption using the Cosmed K5) strength (dynamometer).
7. Those agreeing to exercise/O2 consumption testing will be assessed wearing the Cosmed K5 O2 mask. During their 3rd or 4th treatment session in HELLEN the participants will be assessed wearing the Cosmed K5 mask, during their 30 minute treatment session in HELLEN. This testing will be repeated during their final HELLEN treatment session.
8. Bioelectrical Impedance Analysis to assess changes in body composition.

Participant Timeline

Potential participants will be identified on the MS database by research nurse, [name]. She will then make telephone contact with potential participants to inform them

of the research and gauge their interest in participating. Those interested, will be provided with an information statement detailing the study and will be contacted by [name], in the following week by phone, to answer any questions they may have and if still interested, to arrange a convenient time for an assessment. Once they are deemed eligible, baseline measures will be collected and they will be placed on a 12 week waitlist. These measures will be repeated after the 12 week period, after 6 weeks of intervention, at the conclusion of 6 weeks of intervention and 12-weeks after the intervention period. After the wait period, twice weekly sessions will continue for 12 weeks. They will then be provided with an ongoing home exercise program. In total, participants will be enrolled in the study for 36 weeks.

Sample Size

20 participants with MS will be invited to participate in this pilot trial.

Recruitment

Potential participants will be identified by [name] via the database maintained by the Newcastle MS clinic, MS Base.

Data Collection Methods

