In the event that principle investigator [name] ceases to be engaged with the University of Newcastle, [name] will assume responsibility for the study data.

Statistics

The data collection phase of the trial is expected to take a year. Descriptive statistics, including means and standard deviations (SD), will be calculated for demographic and outcome data. Change scores for each outcome from baseline will be tested using independent t tests for continuous variables and χ^2 tests for categorical variables. Differences from enrolment, baseline, post intervention and 12-week follow up will be evaluated for statistical significance. All analyses will be conducted on an intention-to-treat basis, with missing follow-up data conservatively imputed using the last observation carried forward method. All statistical analysis will be conducted by a qualified statistician.

Descriptive statistics, including means and standard deviations, will be calculated for demographic data. A linear mixed model will be used to detect a significant difference between outcome scores during each time period. The value of the baseline score at the start of the trial and after intervention will be used as a covariate, and analysis conducted to correct for differences in baseline scores and to ensure there is no effect of order. All analyses will be conducted on an intention to treat basis, with missing follow-up data conservatively imputed using the last observation carried forward method.

Data Monitoring

This is a pilot study. No formal interim analysis or DMC is required.

This study will be internally monitored. Chief investigators [name], [name] and [name] will be responsible for ensuring treatment application, data collection, analysis and statistical evaluation are all conducted within accepted scientific practices. Patients will be monitored carefully during the administration of the treatment and adverse events will be documented and submitted to the HREC for evaluation.

Harms

Adverse events will be immediately reported to the ethics committee.

Research Ethics Approval

Application for ethics approval has been given by the Hunter New England Human Research Ethics Committee (17/08/16/4.02).

Protocol Amendments

Protocol amendments affecting future participants will be communicated via a revised participant information form. The research protocol, where necessary, will be revised and disseminated to all relevant parties.

Informed Consent

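### Active harm monitoring covers treatment sessions only; episodic events elsewhere are recorded only if volunteered, so the waitlist cannot be a like-for-like comparator for harm

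*Protocol*

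**What the plan says.** Two sentences in the protocol deal with harms. Data Monitoring: "Patients will be monitored carefully during the administration of the treatment and adverse events will be documented and submitted to the HREC for evaluation". A separate section headed Harms consists of one line: "Adverse events will be immediately reported to the ethics committee". The first ties watching the patient to the giving of treatment. The second sets how fast events are reported. Neither states a collection period or a way of asking.

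Safety is nevertheless a purpose of the study. Background and Rationale expects that "this pilot study will provide the preliminary data required about safety, feasibility and effect size estimates", to support a decision on a larger randomised trial. The Objectives include the device's benefits and applicability, "as well as highlighting any barriers and risks to its potential use in this population".

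The design is "A phase 1 pre-post intervention trial with 12 week baseline control", so each participant's own waitlist is the only control. On treatment, the Intervention section says: "The intervention will involve 2 sessions of exercise therapy per week for 12 weeks". A home exercise program accompanies the sessions, and Participant Timeline says of the period after therapy: "They will then be provided with an ongoing home exercise program". The last assessment in the Outcomes section is "Week 36: Follow-up phase, 12 weeks after completion of intervention".

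**The concern.** Eligibility requires that participants need an aid or another person to be upright. Falls, pain, skin injury and relapse can occur hours or days after a session, at home, or in the two 12-week phases that have no sessions. The plan names nobody to ask about them.

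Two things are at stake. First, a low harm count could reflect lack of enquiry rather than lack of harm. Second, participants meet the therapist far more often in therapy than in the wait. If events come to light mainly through conversation, background MS events are more likely to be noted in therapy and could be read as effects of the device. The waitlist could correct for this, but only if harms are sought there in the same way.

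This is a matter for the protocol. An analysis plan cannot recover events that nobody asked about.

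**Working it through.** The protocol gives no figure for harm ascertainment, so there is none to reproduce. The inputs come from its Intervention, Outcomes, Participant Timeline and Sample Size sections: 2 sessions a week for 12 weeks; up to 1 hour per session, of which half an hour is therapy; assessments at Weeks 0, 12, 18, 24 and 36; 36 weeks in all; 20 participants.

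**1. Time under active observation**
- Sessions: 2 × 12 = 24.
- Hours per participant: 24 × 0.5 = 12 to 24 × 1 = 24.
- Share of the therapy phase: 12 × 168 = 2,016 h, so 12/2,016 = 0.6% to 24/2,016 = 1.2%.
- Share of the whole study: 36 × 168 = 6,048 h, so 12/6,048 = 0.2% to 24/6,048 = 0.4%.
- Weeks with no session: 24 of 36 (67%), including the whole control period.

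These are shares of clock time. They do not estimate the proportion of events that would be recorded.

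**2. Scheduled contact by phase**

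| Phase | Weeks | Scheduled contact after the phase begins |
|---|---|---|
| Wait | 0–12 | one assessment, Week 12 |
| Therapy | 12–24 | 24 sessions, plus assessments at Weeks 18 and 24 |
| Follow-up | 24–36 | one assessment, Week 36 |

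**3. What the listed measures would pick up**

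The Outcomes list includes fatigue (FAS), spasticity (Tardieu), balance, strength, independence, mood and quality of life. Worsening in these that is still present at an assessment would be measured with the same tools in every phase. Falls, relapse, pain and skin injury have no listed item. The gap therefore concerns episodic events.

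**4. Effect of unequal capture (assumed values)**

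Suppose the true event rate is the same in wait and therapy, and fractions c_W and c_T of events are recorded. The observed ratio of therapy to wait is then c_T / c_W. The documents give no capture fractions. Taking c_T = 0.8:
- c_W = 0.8: ratio 1.0
- c_W = 0.5: ratio 1.6
- c_W = 0.2: ratio 4.0
- c_W = 0: no ratio exists

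An apparent excess of 1.6 to 4.0 could thus arise with no effect of the device.

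**5. What equal enquiry would give**

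With full retention, each phase contributes 20 × 12 = 240 participant-weeks. At equal capture and equal true rates the expected ratio is 1.0. No event rate is given, so expected counts cannot be computed. Precision stays limited: 0 affected among 20 leaves a one-sided 95% upper bound of 1 − 0.05^(1/20) = 13.9%, even with complete capture.

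**The case against.** The strongest objection is grammatical. In the Data Monitoring sentence the time limit attaches to watching patients; the clause on documenting events has none, and the Harms sentence has none. A reader might infer that events outside sessions would not be recorded, or would be caught only by chance. The text does not say so. It leaves the window unstated, and a volunteered event would be documented whenever it occurred. This stands, and it limits the claim to the lack of active enquiry.

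Second, twice-weekly contact makes it likely that events between sessions are mentioned during therapy. The Intervention section has the physiotherapist adapt treatment in discussion with the participant and keep the home program under review. This also stands. It narrows the gap in therapy, but it sharpens the contrast with the wait and the follow-up, which have no such contact.

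Third, fatigue and spasticity are already scored in all phases. This stands for lasting change, but not for falls, relapse, pain or injury.

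Fourth, the assessment forms are said to be attached but are not shown. An adverse event item on them would weaken the point. The protocol's own list of measures names none.

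Fifth, the aim is descriptive, and no comparison of harm by phase is planned. That is fair: the trial can describe risks seen in the device, and it goes too far to say that it can tell us nothing about risk. But the waitlist is the design's only control, and without comparable enquiry a therapy-phase count cannot be set against background MS events.

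**Conclusion.** The point holds in a limited form, and the protocol should be changed. Active harm monitoring is stated only for sessions, 12 to 24 hours per participant. Episodic harms at other times depend on being volunteered. The chance to volunteer differs sharply by phase: 24 sessions in therapy against a single closing assessment in the wait and in the follow-up. The waitlist therefore cannot serve as a like-for-like comparator for harm, although safety and risks are stated purposes.

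A reader might infer from the 0.2% to 0.4% that more than 99% of harms would be missed. The documents do not support this: the figure is session time, and events can be reported later. Nor does the design lack a comparator; what is missing is harm collection within it.

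The conclusion assumes that the attached forms carry no adverse event enquiry and that home exercise is done without the therapist present, which is a fair inference but is not stated. The ratios of 1.6 and 4.0 rest on assumed capture fractions and show how the bias could work, not its expected size.

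**What to change.** Add to Data Monitoring / Harms:
- Adverse events are collected from Week 0 to Week 36, whether or not HELLEN sessions have begun or ended.
- One fixed set of questions (falls, relapse, pain or skin injury, unplanned health care) is asked with an identical 12-week look-back at Weeks 12, 24 and 36, so that each enquiry covers exactly one phase.
- These answers are tabulated by wait, therapy and follow-up, per participant-week.
- Any enquiry at Week 18 or at individual sessions is recorded separately as safety surveillance and kept out of the comparison between phases. Week 18 falls halfway through therapy, so a 12-week look-back there would reach into the wait.

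The cost is protocol wording and a short form at visits that already take place. There are four downsides. More background MS events will be recorded. Recall over 12 weeks is imperfect. Asking at sessions may prime recall in the therapy phase, and recording those answers separately does not fully remove this. Finally, the Harms section sends adverse events to the ethics committee at once, so the sponsor must reconcile that sentence with the wider collection.
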